### 1. Abstract

The goal of this study is to reduce preference sensitive, unnecessary daily imaging during radiation treatment in which a pre-planned quality improvement default option for radiation treatment prescriptions will be introduced throughout the network of Penn Radiation Oncology. This study is a pragmatic stepped wedge trial with two comparison groups: (1) a usual practice group (control group) and (2) a default radiation treatment prescription group (intervention group), in which the usual practice group will subsequently rollover from control to intervention so that all sites and physicians in the practice network of Penn Radiation Oncology are exposed to intervention.

## 2. Overall objectives

The purpose of this study is to reduce preference sensitive, unnecessary daily imaging during radiation treatment with the implementations of a quality improvement initiative within 5 sites of Penn Radiation Oncology. We aim to leverage the introduction of a default prescription option to reduce the use of daily imaging in palliative intent cases where it has limited clinical benefit and adds to cost burden. Our objective is to encourage more patient-centric clinical practice.

## 3. Aims

3.1 Primary outcome

The primary objective of this study is to reduce unnecessary daily imaging during palliative radiation treatments.

## 4. Background

4.1 Value-based cancer care. With exponentially rising healthcare costs, providers practice medicine in an increasingly value conscious environment. Physicians are encouraged to reduce low-value care by eliminating unnecessary tests and procedures, thus, reducing healthcare costs at large. However, methods to optimally promote high value care are still under evaluation.

Radiation oncology, in specific, has come under scrutiny for expensive treatments and rising costs particularly with the advent of newer treatment technologies over the past 15 years. We aim to reduce low value care in a multi-site radiation oncology clinical practice.

4.2 Image-guided radiotherapy. Image-guided radiation therapy (IGRT) is a tool used in radiotherapy to ensure reproducible patient positioning during treatment. The two main technologies used to perform IGRT are kilovoltage x-ray images (KV), which are x-ray images to check patient alignment, and conebeam computed tomography (CBCT), which is a CT scan (also 'x-ray' based) done on the radiation treatment table. Regardless of whether IGRT is used, all patients have daily clinical positioning using immobilization devices and a calibrated treatment table with 3-dimensional lasers aligned to small tattoos placed on the body at the time of treatment planning.

The role of IGRT is evolving in the field of radiation oncology. While evidence for its clinical utility is uncertain or even limited in certain clinical situations, IGRT is used extensively amongst radiation oncologists and its use is projected to increase further. However, daily imaging beyond clinical positioning adds significant additional radiation exposure and increases the total time on the treatment table for patients who are often in pain or have limited mobility.

Given the limited evidence and lack of clarity regarding ideal use of IGRT, and the fact that all patients receive daily clinical positioning, insurance companies are increasingly denying the charges associated with such procedures. Furthermore, daily IGRT also places a considerable strain on clinic resources and efficiency.

Overuse of IGRT is particularly apparent during palliative radiation treatments. Our department has demonstrated that for the palliative treatment of brain metastases standard, clinical immobilization and setup techniques without the use of daily IGRT are sufficient for treatment in routine cases. Moreover, evidence-based guidelines clearly state that "IGRT generally is not medically necessary in the palliative setting." Yet despite uncertain clinical need and decreasing reimbursements, physicians often reflexively order daily imaging for treatment.

4.3. Preliminary data. At our institution, across the University of Pennsylvania Health System (UPHS) Radiation Oncology network, 79% of palliative intent radiation courses over the past year (August 2015 – August 2016) utilized daily x-ray image guidance as part of the treatment paradigm. As shown in Table 1, despite clinical guidelines recommending against the use of daily IGRT in palliative cases, 83% of bone metastases, 82% of soft tissue metastases, and 57% of palliative brain/ CNS cases employed daily IGRT during the associated radiation treatment course.

Palliative Type	Total N	% Courses w Daily IGRT
Bone	459	83.4%
Brain/ CNS	133	57.1%
Soft Tissue	216	82.4%
Unknown	2	50.0%
SBRT	21	100.0%

Table 1: Use of Daily IGRT in Palliative Cases at UPHS by Treatment Indication

\*Daily IGRT defined as at least 80% (i.e., 4 of 5 days, on average) of treated fractions in a treatment course have IGRT

\*\*SBRT: Stereotactic Body Radiation Therapy

As shown in Table 2, the total number of palliative courses and associated daily IGRT varies across our main site and satellites. Our main site, the Perelman Center for Advanced Medicine (PCAM), has the highest volume of cases overall, and, hence, the highest number of palliative courses. All sites across the UPHS radiation oncology network, however, demonstrate high levels of daily IGRT usage in palliative courses. Over the past year, the number of palliative courses treated at each department was roughly stable over time as shown in Table 3, other than a slight rise in the number of cases treated during the month of June.

[figure not shown]
Location	Total N	% Courses w Daily IGRT
PCAM	623	81.4%
PAH	56	58.9%
СНН	39	79.5%
DH	55	76.4%
VF	52	80.8%
Unknown	6	66.7%
Grand Total	831	79.3%

**Table 2:** Use of Daily IGRT in Palliative Cases by UPHS Radiation Oncology Department

 Location

**\*\***PCAM: Perelman Center for Advanced Medicine; PAH: Pennsylvania Hospital; CHH: Chestnut Hill Hospital; DH: Doylestown Hospital; VF: Valley Forge

 Table 3: Monthly Frequency of Palliative Courses

\*PCAM: Perelman Center for Advanced Medicine

\*\*Non-PCAM consists of satellites at Pennsylvania Hospital, Chestnut Hill Hospital, Doylestown Hospital, and Valley Forge

4.4. Default options. We have described how default options can be an effective means of reducing low-value services in cancer care and other healthcare settings. Defaults may promote high-value care by introducing a treatment standard indicative of evidence-based guidelines or institutional recommendations. For instance, in our own health system, a change in default drug prescription options in the electronic health record (EHR) has been successfully leveraged to reduce the prescription of low-value, brand name medications. *Default options* 

provide a unique means of influencing decision-making while preserving physician choice; importantly, default prescriptions may be altered by treating physicians to best serve the needs of their patients.

At Penn Radiation Oncology, default prescriptions for radiation are the norm. These defaults exist currently in non-palliative settings and involve template prescription order sets that contain default settings. These default prescription templates improve clinic workflow and standardize clinical care. Importantly, as always with default prescription options, physician choice is preserved.

In the initiative proposed herein, we aim to introduce a default prescription template in the palliative setting. This effort is part of the department's overarching quality improvement initiative to standardize treatment approaches. With defaults, the physician has the option to alter default order sets to fit their clinical decisions. This is true for all other default prescription order sets already in use in our clinic. In other words, default options for curative, non-palliative treatments are currently standard of care in our clinic as a means of improving efficiency and standardizing care across our network, and we plan to rollout default options for palliative treatments in order to reduce unnecessary daily image guided radiation.

4.5 Quality Improvement Initiatives in the Radiation Oncology Department: The Penn Medicine Department of Radiation Oncology (also called Penn Radiation Oncology) has a long history of excellence in quality improvement and safety initiatives. QI initiatives are typically implemented first at either PCAM or non-PCAM sites and then rolled out to the entire clinical practice. Continuous quality improvement is conducted though monitoring and comparisons of physician and site rates of care delivery, depending on the focus of the QI initiative, and iterative changes to improve initiatives are then implemented over time. In this study, we leverage the existing departmental processes for QI implementation, and we will choose the first site of intervention implementation by coin flip rather than arbitrarily as has been done in the past.

Our study is sponsored and approved by our health systems partners including the Office of the Chair of Radiation Oncology and the Penn Medicine Nudge Unit.

## 5. Study design

## 5.1 Design

In this study, we propose to leverage a pre-planned departmental initiative of default prescriptions to reduce unnecessary daily x-ray imaging in palliative radiation treatments.

This study follows a pragmatic stepped wedge design with two comparison groups: (1) a usual practice group (control group) and (2) a default radiation treatment prescription group (intervention group), in which the usual practice group will subsequently rollover from control to intervention. One group is comprised of physicians who practice at the Perelman Center for Advanced Medicine (PCAM). Another group is comprised of non-PCAM physicians at our network satellites (Pennsylvania Hospital, Chestnut Hill Hospital, Doylestown Hospital, and Valley Forge). As is standard practice for implementation of QI initiatives in our department, we will implement the intervention at one network site prior to implementing the intervention at all

[figure not shown]
sites. These groups will be assigned to the intervention or usual care at the start of the study by coin flip. Subsequently, the usual practice group will rollover into the default intervention.

Intervention. The default intervention will be started in February 2017. It will be comprised of default prescription order sets that do not include daily imaging for brain/ CNS, bone, and soft tissue metastases (See Figure 1). The defaults will be immediately preceded by a department wide session with intervention group physicians and therapy staff announcing the initiation of the intervention. Thus, as is usual practice in the department, physicians and department staff will be aware and educated on the QI initiative at the time of implementation. Default prescription order sets will be created in Aria (the radiation oncology electronic health record) for specific palliative treatment indications, namely brain/CNS, bone, soft tissue, and other palliative cases.

IGRT-LOCALIZATION INSTRUCTIONS:		
PRIMARY (Match for Treatment)	SECONDARY (EVAL)	
Modality: None	Modality: None	
Frequency: Other	Frequency: Other	
Match Instructions: Set up with attention to immobilization, tattoo markers, and weekly MV portal films	Additional / Special Instructions:	
Additional / Special Instructions: do not take KV-KV image		
Localization Instructions For CD Or Other If Different From Initial:		

Figure 1: Example of Default IGRT Prescription for Palliative Cases

Figure 2: Study Framework

\*Coin flip to determine initial intervention vs. usual care group: Group 1: PCAM Physicians Group 2: Non-PCAM Physicians (Pennsylvania Hospital, Chestnut Hill Hospital, Doylestown Hospital, and Valley Forge)

The study will involve our entire physician network across the UPHS Radiation Oncology network, including both PCAM and regional network facilities (Pennsylvania Hospital, Chestnut Hill Hospital, Doylestown Hospital, and Valley Forge).

## 5.2 Study duration

The duration of the study will be 27 months, including the 12 retrospective pre-intervention study period, 1 month for the intervention, 2 months for the first post-intervention study period, 1 month for the control to cross over to the intervention, and 2 additional months for observation in which all physicians are exposed. Analysis of data and dissemination of results will occur in the 9 month period following the  $2^{nd}$  post-intervention period.

# 5.3 Target population

The study will include a total of ~29 subjects (UPHS radiation oncologists) and 5 sites across the UPHS network (Perelman Center for Advanced Medicine, Pennsylvania Hospital, Chestnut Hill Hospital, Doylestown Hospital, and Valley Forge) that treat about 800 palliative patients a year. The University of Pennsylvania Radiation Oncology network (both PCAM and satellites) will be the only site of this study.

## 5.4 Accrual

Radiation oncology physicians will be recruited from the University of Pennsylvania Health System.

## 5.5 Key inclusion criteria

- Radiation treatment courses with palliative intent
- Palliative treatment of bone, soft tissue, and intracranial metastases
- Photon radiation with 3D conformal therapy (3DCRT) only

## 5.6 Key exclusion criteria

- Use of intensity modulated radiation (IMRT) or stereotactic body radiation (SBRT) as radiation treatment modality
- Retreatment to same site
- Proton radiation

## 6. Subject recruitment

Not applicable. Subjects will include all UPHS radiation oncologists. As a result, no recruitment will be needed in this study.

## 7. Subject compensation

No compensation will be offered in this study.

## 8. Study procedures

#### 8.1 Consent

A waiver of informed consent is requested. This is a departmental quality improvement initiative that will be implemented regardless of the study we propose. The study is to evaluate that quality improvement initiative. Without a waiver of the consent, the initiative would still be implemented by the health system, but the study would be infeasible. Additionally, consenting every patient and physician would make the study impossible to conduct. As mentioned, this initiative would occur with or without the study of it. Furthermore, if physician members of the usual care group were consented, they would know they were being studied and this could bias their behavior, which would make our findings difficult to interpret. Moreover, physicians are not being forced to change their prescription of image guidance in radiation. Instead, they are being reminded of evidence-based guidelines and offered a default option which can be altered. The physician would continue to prescribe radiation treatment and whichever imaging they believe is appropriate for the patient. The intervention is simply a default option for the physician and makes their care process easier to conduct.

#### 8.2 Procedures

Data on use of daily imaging will be obtained from Aria. De-identified patient-level demographic and disease-specific data will also be obtained from EPIC, including patient age, race, gender, cancer diagnosis, and insurance provider. Billing information associated with the IGRT CPT codes used in the pre and post-intervention radiation courses will be obtained from our revenues department.

## 8.3 Coin-flip to select initial site (randomization)

Group 1 (PCAM physicians) and 2 (non-PCAM physicians) will be assigned to either the intervention or control group prior to study initiation by coin flip (rather than arbitrarily as has been done in past QI efforts). The control group will then rollover to the intervention arm after 2 months.

## 9. Analysis plan

The primary analysis will use a mixed effects logistic regression model, where the unit of analysis is an individual patient, the outcome is use of daily x-ray imaging and the explanatory variables are time (pre-intervention vs. post-intervention period), dummy variable for whether the intervention is received, group (PCAM vs. satellite providers) and physician random effects. The coefficient of interest is the coefficient of whether the intervention is received. The physician random effects account for the clustering by physician. The study is analyzed at the physician level (patients clustered within physicians) rather than the practices site level because there are only two practice sites. Of the two practice sites – PCAM vs. non-PCAM sites – one group will be assigned to the intervention for the entire intervention period by coin flip, and the other group of providers will be assigned to the control for the first two months of the intervention. Randomly assigning the order of practice sites exposed to the intervention helps to blunt selection bias. For this analysis, we have 89% power to detect an effect of the intervention that reduces the probability of daily imaging by 0.2 for each physician.

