#### i. Intervention arm (Perelman Center for Advanced Medicine - PCAM)

- 1. 2/10/2017-3/9/2017: 1 month roll out
  - a. Intervention announced to entire group at faculty meeting and by email
  - b. Individual meetings with intervention group attendings to assure awareness and use of default prescription order
  - c. Educational meetings with therapists to introduce new default prescription
- 2. 3/10/2017-6/9/2017: 3 month intervention period
  - Only the intervention arm (PCAM) has access to the default option and the usual practice group (satellites) does not undergo the intervention
- 3. 6/10/2017-10/10/2017: Crossover period
  - a. Default intervention is introduced to usual care group.
- Intervention group continues to practice without any change.
- ii. Usual practice / control group (Pennsylvania Hospital, Chestnut Hill,

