# 4. Outcome measures

- a. Primary Outcome
  - i. Change in daily IGRT use from baseline pre-intervention period to intervention periods within the control and intervention arms
    - 1. Daily IGRT defined as at least 80% (i.e., 4 of 5 days, on average) of treated fractions in a treatment course have image guidance
  - ii. Change in daily IGRT use between control and intervention arms during first intervention period (3/10/17-6/9/17)

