#### b. Rate of images per total fractions (outcome as continuous variable)

- i. Change in rate of images per total fractions taken pre and post intervention in each arm with 95% CI and p values
  - 1. Calculate this separately for PCAM vs. satellites
    - a. PCAM: pre intervention (2/10/16-2/9/17) vs. post intervention (3/10/17-10/10/17)
    - Satellites: pre intervention (2/10/16-6/9/17) vs. post intervention (7/10/17-10/10/17)

Commented [DMG2]: Would make cohort columns to compare populations

Should look like this for example:				
	PCAM		Satellite	
	Pre	Post	Pre	Post
Race				
Age				

**Commented [SS3]:** Excludes the 1 month roll out period (2/10/17-3/9/17)

JB: Make sure [name] agrees \*\*

10/15/17 Update: [name] agrees that we should exclude roll out month

**Commented [SS4]:** Does preintervention period for control group end 2/9/17 or 6/9/17?

Need to confirm w [name]\*\*

10/15/17 Update: [name] says preintervention period ends 6/9/17 for satellites

**Commented [SS5]:** Excludes 1 month roll out (6/10/17-7/9/17)

SS: Confirm with [name]\*\*

10/15/17 Update: [name] agrees that we should exclude roll out month

 Change in rate of images per total fractions between PCAM (intervention group) and satellites (control group) during first intervention period (3/10/17-6/9/17)

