#### b. Primary model + relevant patient level factors

- 1. Intervention
  - 2. Attending (clustering at level of attending)
  - 3. Location
  - 4. Time?
  - 5. Age
  - 6. ECOG
  - 7. Prior radiation
  - 8. Insurance type (Commercial, Medicare , Medicaid, Uninsured, Unknown)
  - 9. Total number of fractions per course
- c. Sensitivity model
  - i. Covariates:
    - 1. Cohort (intervention vs. control arms)
    - 2. Age
    - 3. Sex
    - 4. Race
    - 5. ECOG
    - 6. Insurance type (Commercial, Medicare , Medicaid, Uninsured, Unknown)
    - 7. Target type (Brain, bone, soft tissue, multiple sites, other)
    - 8. Prior radiation (course 1 vs. not course 1)
    - 9. Total number of fractions per course

Commented [SS6]: Time defined as days from intervention?

- 10. Dose per fraction
- 11. Attending
- 12. Time of day
- 13. Location (PCAM vs. satellite)
- d. Assess missing data
- e. Unadjusted and adjusted analyses for covariates in relation to primary outcome (daily IGRT use)

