#### Methods:

For the main analysis model, we used PROC GENMOD to fit models based on generalized estimating equations with a logit link and an independence correlation structure using the attending physician as the clustering unit with month and site as covariates. In sensitivity analyses, the main model was estimated by also adjusting for patient characteristics including age, sex, race,...,..,etc.

To obtain the adjusted difference in the percentage of patients receiving daily IGRT imaging between intervention and non-intervention groups and 95% confidence intervals (CIs), we used the bootstrap method, resampling patients 1000 times. Resampling of patients was by physician to maintain clustering at the physician level. All analyses were conducted in SAS version 9.4.

7

**Commented [SS7]:** CR: Note: It's possible we might use a different correlation structure. We can modify what goes in the list of the covariates for the sensitivity model.

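### Protocol section 9 gives both post-launch steps a single time effect although the second group crosses over between them, and the SAP's undefined month term does not settle the coding

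*Protocol*

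**What the plan says.** Protocol section 9 specifies a mixed effects logistic model in which "the explanatory variables are time (pre-intervention vs. post-intervention period), dummy variable for whether the intervention is received", with group and physician random effects. The intervention coefficient is the target. The same section claims that "we have 89% power to detect an effect of the intervention that reduces the probability of daily imaging by 0.2".

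The order was open when the protocol was written: the groups "will be assigned to either the intervention or control group prior to study initiation by coin flip" (section 8.3). Section 5.2 gives 12 retrospective months, then a roll-out month and a 2-month step, twice.

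The SAP names PCAM as the first group and lengthens the steps ("3/10/2017-6/9/2017: 3 month intervention period"). It treats time in three ways:
- The primary adjusted model (section 3.a) lists time without a definition.
- The model with patient factors (section 3.b) lists time with a question mark. A margin comment asks, without a recorded answer, "Time defined as days from intervention".
- The Methods text describes GEE with "an independence correlation structure using the attending physician as the clustering unit with month and site as covariates".

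The roll-out rule ("Excludes the 1 month roll out period (2/10/17-3/9/17", and likewise the satellites' own roll-out month) is attached to the unadjusted analyses only.

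**The concern.** The post level in section 9 must be a calendar period. If it were specific to each arm it would equal the intervention dummy, and the model could not be fitted. One level therefore covers a step in which the second group is unexposed and a step in which it is exposed. A change common to both steps is absorbed. A change between them is not: most of it is read as an effect of the default. Physician random effects do not help, because they absorb differences between physicians and not calendar change.

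Some drift is conceivable, since protocol section 4.2 says that insurers increasingly deny IGRT charges. The SAP's month term could remove the problem or only part of it, depending on a form that it does not state. That choice also moves the standard error by a factor of about 1.7, so it should not stay open once data are in hand.

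**Working it through.** **Inputs.** Table 2: PCAM 623 courses a year; satellites 56+39+55+52 = 202; shares 623/825 = 0.7552 and 0.2448. Baseline daily IGRT: PCAM 81.4%; satellites (56×58.9+39×79.5+55×76.4+52×80.8)/202 = 73.3%. Twelve pre-intervention months; steps of 2+2 months (protocol) or 3+3 (SAP), each preceded by a roll-out month. Effect 0.20. Assumed: two-sided 5%, no clustering in the linear approximation. Roll-out months are dropped either from both arms or only from the arm rolling out (the SAP's rule).

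**1. The 89%.** It cannot be reproduced: alpha, sidedness, intraclass correlation, order and courses per step are not given. With pre/post coding at 2+2, the linear approximation gives 63–77% with PCAM first and 95–98% with satellites first, so 89% lies between the two orders. A simulated random-intercept logistic model with PCAM first (400 runs per setting; assumed 20 and 9 physicians, physician SD 0.3–1.2 on the logit scale) gives 54–66% two-sided and 70–76% one-sided at 2+2, and 74–81% and 85–91% at 3+3.

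**2. Share of a step-2 shift entering the coefficient, pre/post coding.** The coefficient weights each group-by-period cell by its courses times the residual of the intervention indicator after group and time. For 3+3, PCAM first, both roll-out months out of both arms:
- Mean exposure: PCAM 6/18 = 0.3333; satellites 3/18 = 0.1667; post period 0.7552 + 0.2448/2 = 0.8776; overall 0.2925.
- Residuals: PCAM post 1 − 0.3333 − 0.8776 + 0.2925 = 0.0816; satellites step 2 1 − 0.1667 − 0.8776 + 0.2925 = 0.2482.
- Denominator: 0.7552×6×0.0816 + 0.2448×3×0.2482 = 0.3697 + 0.1823 = 0.5520.
- Step-2 part: 0.7552×3×0.0816 + 0.1823 = 0.3672.
- Share: 0.3672/0.5520 = 0.665.

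The other cases, by the same weighted least squares:

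| Order | Steps | Both-arm exclusion | Own-arm exclusion |
|---|---|---|---|
| PCAM first | 2+2 | 0.638 | 0.704 |
| PCAM first | 3+3 | 0.665 | 0.708 |
| Satellites first | 2+2 | 0.845 | 0.863 |
| Satellites first | 3+3 | 0.860 | 0.872 |

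**3. Effect of a steady trend.** With both-arm exclusion the bias is the share times the gap between step midpoints: 0.665 × 4 months = 2.66 points per 1 point/month at 3+3. Across the PCAM-first cases it is 1.9–3.1 points; for an assumed 0.5–2 points/month, 1.0–6.3 points.

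**4. Other time terms, 3+3, PCAM first.**
- Linear month: 0 for a linear trend; 0.350 (both-arm) or 0.415 (own-arm) of a step-2-only shift.
- Days from each arm's own start, signed: the same as linear month once site is in the model.
- Categorical month: 0 for any shift common to both groups.
- Pre / step 1 / step 2: 0 with both-arm exclusion; with own-arm exclusion, 0 for a step-2-only shift but about 0.6 points per 1 point/month.

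On the logit scale (own-arm exclusion, no true effect, common 5-point fall in step 2), the false risk difference is −3.5 points with pre/post, −2.1 with linear month and +0.2 with categorical month. The last is scale mismatch.

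**5. Precision.** With categorical month, the estimate is the PCAM-minus-satellite difference in step 1 less the average difference over the other months (weights 12/15 and 3/15 at 3+3). Variances at 3+3, with exposed rates 0.20 lower:
- Step 1: 0.614×0.386/155.75 + 0.733×0.267/50.5 = 0.00152 + 0.00388.
- Other months: 0.64×0.00121 + 0.04×0.00645 = 0.00103.
- SE = √0.00643 = 0.080; power = Φ(0.20/0.0802 − 1.96) = Φ(0.53) = 70%.

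| Case | Pre/post | Categorical month |
|---|---|---|
| 3+3, PCAM first | SE 0.065–0.073, power 78–86% | SE 0.080, power 70% |
| 3+3, satellites first | SE 0.042–0.045, power 99% | SE 0.083, power 67% |
| 2+2, PCAM first | power 63–77% | power 55% |
| 2+2, satellites first | power 95–98% | power 52% |

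Linear month at 3+3, PCAM first: SE 0.046–0.047, power 99%. One-sided power with categorical month at 2+2 is 64–67%. Table 2 includes courses that section 5.6 excludes, such as SBRT, so actual standard errors would be larger.

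**The case against.** **The SAP has already dropped pre/post coding.** This stands in part. The shares in step 2 of the working apply to the protocol's model, and a reader might infer that the SAP's main analysis carries them. It does not: under either form of month, a linear trend gives no bias. What stays open in the SAP is the form of month and the unanswered comment.

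**The harm is conditional.** This stands. No trend in daily IGRT is reported; the stability noted in protocol section 4.3 concerns case volume. With no true effect and an assumed 5-point common fall, pre/post coding rejected in 4–7% of simulated trials, close to nominal. A 10-point fall gave 9–18%, against 3–5% with three periods (3-month steps at SD 0.3 and 0.7 only).

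**Categorical month is costly, and linear month may have the smaller total error.** This stands as arithmetic. For a 5-point step-2-only shift at 3+3, PCAM first, linear month has root mean square error √(0.0473² + (0.350×0.05)²) = 0.050, against 0.080. But that precision is bought with a linearity assumption over 20 months that nothing in the documents supports. Three-period coding is also a legitimate choice: under own-arm exclusion its SE is 0.074 (power 77%), with the small residual trend bias shown above.

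**One primary comparison avoids the problem.** This stands. SAP section 4.a.ii lists "Change in daily IGRT use between control and intervention arms during first intervention period (3/10/17-6/9/17" as part of the primary outcome. It uses no step-2 data. It is not, however, the main model.

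**Conclusion.** Protocol section 9 fits a time term that does not match its stepped design. Under that model, 64–71% (PCAM first) or 84–87% (satellites first) of a common change between the steps enters the intervention coefficient. The SAP improves on this but leaves the term undefined, and linear month would still pass on 35–42% of a step-2-only shift at 3+3 with PCAM first. These figures rest on a linear approximation, Table 2 volumes and 12 pre-intervention months.

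Three stronger readings are not supported:
- That the trial's estimate is biased. This needs a drift that the documents do not show; against a 20-point target, an assumed 1 point/month gives 1.9–3.1 points under the protocol's coding with PCAM first.
- That the 89% is wrong for the protocol's own model. Its inputs are missing, and values near it arise under some orders and step lengths. What can be said is that 2+2 months do not reach 89% once the steps are separated.
- That categorical month removes all time bias. It removes only shifts common to both groups on the model scale. With two groups, no common time term deals with differential drift.

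No size is attached to the days-from-intervention idea with time set to zero before the start, because the SAP does not state that coding.

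**What to change.** State one calendar-time term, worded identically in protocol section 9, SAP sections 3.a and 3.b, and the SAP Methods text, that separates step 1 from step 2. Either:
- categorical calendar month, cut from the 10th to the 9th so that months match the SAP's windows; or
- pre / step 1 / step 2, with both roll-out months excluded from both arms.

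Delete the days-from-intervention option and keep linear month as a sensitivity analysis at most. State that the roll-out exclusion also applies to the adjusted model. Recompute the power for the chosen model and restate it with order, step length, alpha, sidedness and physician clustering.

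The cost is wording, one new power calculation and precision. At 3+3 with PCAM first, the SE with categorical month is 1.10 to 1.23 times that with pre/post coding and about 1.7 times that with linear month. With satellites first it is roughly double the pre/post value. Three periods with both-arm exclusion have the same SE as categorical month. Categorical month also brings about 20 parameters (20 months from 2/10/16 to 10/10/17) into a model with about 29 physician clusters, which the three-period version avoids.
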